### **Paradigm 2 – suppression of hyper-activated networks**

Cathodal tDCS will be applied (i) to the posterior DMN in bvFTD patients to inhibit DMN connectivity, and (ii) to the anterior SN in AD patients to inhibit SN connectivity.

#### **Outcome measures**

We will test whether the suppression of AD and bvFTD anti-correlated networks improves clinical condition.

PRIMARY and SECONDARY efficacy parameters will be the same as in AIM1.

### **Aim3**

To elucidate the mechanisms underlying network recalibration, in vivo biomarkers of structural and functional networks connectivity will be collected off-line. Each subjects will undergo an MRI scan on a 3T scanner at the UO3. The following sequences will be collected:

- resting-state functional MRI (rs-fMRI), to assess DMN and SN functional connectivity
- arterial spin labelling (ASL), to measure DMN and SN brain perfusion
- diffusion tensor imaging (DTI), to measure DMN and SN structural connectivity
- structural MRI, for the routine assessment of cortical and hippocampal atrophy

Scan will be collected at baseline (T0, prior to tDCS experiment), after completion of the tDCS sessions (T1), and after 6 months (T2). The subjects included in this analysis will be those recruited for AIM1 and AIM2 (20 AD and 20 bvFTD).

### **Outcome measures**

We will identify (surrogate) imaging biomarkers of DMN and SN recalibration in AD and bvFTD.

Surrogate primary outcome measures will be:

- change at T1 compared with T0 for rs-fMRI DMN and SN connectivity
- change at T1 compared with T0 for ASL DMN and SN connectivity

Surrogate secondary outcome measures will be:

- change at T1 compared with T0 for DMN and SN structural connectivity
- change at T2 compared with T0 for rs-fMRI, ASL, and DTI connectivity biomarkers

### **Control group**

For baseline comparison of clinical, cognitive, and imaging variables, a group of 20 cognitively healthy controls of comparable age will be recruited. Controls will undergo the same clinical, neuropsychological and MRI assessment of patients at baseline.

### **d. Preliminary data**

In a recent review, we observed that AD and bvFTD target distinct large-scale brain networks (Pievani et al., *Lancet Neurol* 2011). Using modern imaging techniques, such as rs-fMRI and diffusion tensor imaging (DTI), we showed that structural and functional connectivity is disrupted along specific networks in AD and FTD (Pievani et al., *Hum Brain Map* 2010; Pievani et al., *Alzheimer's Dementia* 2014). Our lab previously used rs-fMRI to investigate the effect of pharmacological interventions on DMN connectivity in AD patients (Lorenzi et al., *Drugs Aging* 2011). We previously used brain stimulation to modulate cognition in AD and FTD (Manenti et al., *Brain Stimulation* 2012; *Behav Brain Res* 2011; Cotelli et al., *Eur J Neurol.* 2012; *Neurocase* 2012), showing that the beneficial effects of brain stimulation in AD are still present 12 weeks after intervention (Cotelli et al., *JNNP* 2011). Previous experience also includes the combination of fMRI and brain stimulation techniques to modulate neural networks underlying memory (Manenti et al., *Brain Topogr* 2010).

### **e. Methodologies and Statistical Analyses**

#### **Clinical assessment**

Severity of dementia will be assessed with the Clinical Dementia Rating (CDR) scale (Hughes et al., 1982), behavioural symptoms with the neuropsychiatric inventory (NPI) scale (Cummings et al., 1994). The neuropsychological assessment will include the MMSE and specific tests for each cognitive domain (Rey's word list immediate and delayed recall, Rey figure delayed recall, logical memory test immediate and delayed recall, digit span test backward and forward for memory; Rey figure copy for visuospatial abilities, letter and category fluency for language, token test for comprehension, and Trail

Making Test for executive functions; Reading the mind in the Eyes Test, 60 Ekman faces Test for emotions recognition).

### **tDCS experiment**

Patients will receive 25-minute treatment sessions five consecutive days a week for two weeks. tDCS will be delivered (anodal or cathodal at 2 mA) by a battery-driven stimulator through two pairs of saline-soaked sponge electrodes, placed over the left and right inferior parietal cortex (for the DMN), and the left and right prefrontal cortex (for SN). The reference electrodes will be fixed on the contralateral supraorbital area.

### **MRI sequences**

- echo planar imaging (EPI) sequence for rs-fMRI analysis (TR/TE=2700/30ms, flip angle=85°, matrix size=64x64, FOV=192x192mm, 40 axial slices, slice thickness 3 mm, 200 volumes);
- single post-label delay (PLD) pseudo-continuous ASL (pCASL) for ASL analysis (128x128x25mm^3; TR/TE=4000/16ms; 1650ms label duration; 1525ms PLD; 160 averages);
- spin echo echo-planar imaging (SE-EPI) for DTI analysis (TR/TE=9300/87ms, slice thickness 2 mm, no gap, matrix size=128x128, FOV=256x256mm), with 5 b0 images (b factor = 0 s/mm^2), and 30 gradient directions (b=700 s/mm^2);
- 3D MPRAGE for cortical thickness and hippocampal atrophy measurement (TR/TE/IT=2300/3/900ms, slice thickness 1 mm, matrix size=240x240, FOV=256x256mm).

### **MRI analyses**

- Resting-state connectivity in the DMN and SN will be analyzed at T0, T1, and T2 with Independent Component Analysis (ICA), according to procedures previously described (Agosta et al., 2012).
- Brain perfusion will be quantified on pCASL through the application of a modified monocompartment model to obtain whole brain CBF maps (Buxton et al., 1998). Brain perfusion will be measured in the DMN and SN through a regions-of-interest analysis. In addition, a data driven ICA analysis will be applied for the automated extraction of these networks.
- White matter (WM) tracts connectivity will be assessed on DTI scans using previously described procedures (Pievani et al., 2010). Briefly, WM tracts connecting DMN and SN nodes (anterior and posterior cingulum, parahippocampal gyrs, SLF) will be reconstructed and biomarkers of fractional anisotropy, mean diffusivity, axial and radial diffusivity will be assessed.
- Cortical thickness will be measured on structural MRI with FreeSurfer (Fischl and Dale, 2000), hippocampal atrophy with manual tracing according to previously described procedures (Pievani et al., 2011b).

### **Biological samples (optional sub-study)**

Levels of Abeta42, total tau, and phospho-tau proteins will be determined at baseline by commercially available enzyme linked immunosorbent assay (Innogenetics, Belgium). CSF levels will be defined as normal/abnormal according to the normative values of Sjogren and colleagues (Sjogren et al., Clin Chem 2001). DNA extraction and APOE genotyping will be carried out on blood samples according to procedures previously described (Pievani et al., 2011b). DNA extraction will be carried out on blood cells through miRNA Blood PaxGene kit to measure changes in peripheral inflammatory markers (a panel of pro-inflammatory (IL-6, IL-1beta, TNF-alpha) and anti-inflammatory (IL-10) cytokines) following intervention, using gene expression analysis in Real Time PCR.

### **Statistical analysis**

Sample size for this pilot study (n=10 subjects for each experimental group) has been determined on the basis of previous tDCS (Cotelli et al., 2011) and rs-fMRI studies (Lorenzi et al., 2011; Pievani et al., Alzheimer's Dementia 2014) of the Consortium.

Paired t-tests will be used to compare pre-treatment (T0) *versus* post-treatment (T1, and T2) variables in each treatment group (AD and bvFTD).

Correlations between clinical/cognitive changes and imaging biomarkers will be assessed with Pearson's correlation coefficient.

Two-sample t-tests will be used for cross-sectional comparisons of clinical/cognitive scores between paradigm 1 and 2 (i.e. network stimulation *versus* network inhibition) in the experimental groups and to evaluate differences in clinical, cognitive, and neuroimaging measures between the experimental groups and controls at baseline.

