#### **c. Experimental design**

##### **Aim 1**

##### **Population study**

Twenty patients (10 mild AD and 10 mild bvFTD) will be recruited at the IRCCS-Fatebenefratelli of Brescia. Inclusion criteria will be a diagnosis of AD or bvFTD according to the current clinical criteria (Albert et al., 2011; Rascovsky et al., 2011) and ability to provide written informed consent. Exclusion criteria will be moderate/severe dementia (MMSE<18) and/or the presence of any medical or psychiatric illness that could interfere in completing assessments.

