### **Paradigm 1 - direct stimulation of disconnected networks**

The DMN is anchored to `posterior` regions and the SN is anchored to `anterior` regions (Zhou et al., 2010). DMN connectivity will be stimulated in AD patients through anodal tDCS of the posterior DMN; SN connectivity will be stimulated in bvFTD patients through anodal tDCS of the anterior SN.

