#### **Outcome measures**

We will test whether the stimulation of AD- and bvFTD-disrupted networks improves patients clinical condition.

PRIMARY efficacy parameters will be:

- change in scores at T1 compared with T0 for clinical and behavioural scores in AD and bvFTD patients

SECONDARY outcome measures will be:

- change in scores at T1 compared with T0 for cognitive performance in AD and bvFTD patients
- change in scores at T2 compared with T0 for clinical, behavioural, and cognitive performance in AD and bvFTD patients

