#### **Population study and clinical assessment**

Ten mild AD and 10 mild bvFTD patients will be recruited and assessed following the procedures and inclusion/exclusion criteria described in AIM1. Patients will be evaluated at baseline (T0), after tDCS sessions (T1), and after 6 months (T2).

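### The only planned comparison of stimulation with suppression is cross-sectional, so it does not estimate whether change from T0 differs between the two paradigms

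*Combined protocol and SAP*

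**What the plan says.** Aim 1 recruits one set of patients for anodal stimulation: "Twenty patients (10 mild AD and 10 mild bvFTD) will be recruited". Aim 2 recruits a second set for cathodal suppression: "Ten mild AD and 10 mild bvFTD patients will be recruited and assessed following the procedures". Within a diagnosis the paradigms differ in polarity and in target network. For AD, paradigm 1 reads "DMN connectivity will be stimulated in AD patients through anodal tDCS of the posterior DMN", while paradigm 2 applies cathodal current "to the anterior SN in AD patients to inhibit SN connectivity".

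The primary outcome under Aim 1 is "change in scores at T1 compared with T0 for clinical and behavioural scores in AD and bvFTD patients", and Aim 2 uses the same outcomes.

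The Statistical analysis section (B.e) then gives:

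- the size: "Sample size for this pilot study (n=10 subjects for each experimental group");
- paired t-tests of T0 against T1 and T2 for "variables in each treatment group (AD and bvFTD");
- the one test between paradigms: "Two-sample t-tests will be used for cross-sectional comparisons of clinical/cognitive scores between paradigm 1 and 2".

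That last sentence names no visit, mentions no T0 value or change score, and does not say outright that the test is done separately in AD and in bvFTD. The same sentence goes on to compare patients with controls at baseline, and there it adds neuroimaging.

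**The concern.** The outcomes are changes from T0, but the paradigm comparison is of scores at one time. A score at T1 or T2 contains the patient's starting level as well as the change. With 10 patients per paradigm, a difference in scores after treatment can simply be the difference that was there at T0.

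The documents describe no method of allocating patients to the paradigms. Section G has a first patient completing tDCS sessions in Month 1 under each paradigm, so the two run side by side. Equal T0 means therefore cannot be taken for granted. T0 is measured in every patient, so the planned test leaves aside information that the trial already holds. At stake is a wrong statement that stimulation works better or worse than suppression, or a real difference missed.

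A smaller matter is the paired-test label, which gives the diagnosis but not the paradigm.

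**Working it through.** **Head count.** 2 diagnoses × 2 paradigms × 10 = 40, which agrees with the 20 AD and 20 bvFTD under Aim 3. The choice of 10 cannot be reproduced: the section refers to earlier studies and gives no alpha, power, effect size, SD or correlation.

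**Assumptions (mine).** Two-sided alpha 0.05; 10 per paradigm within one diagnosis, all with T0 and T1; between-patient SD 1 at both visits; T0–T1 correlation r; the planned test done at T1.

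**What each test estimates.** Let the true difference in mean change be D and the true T0 gap be G.

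- Cross-sectional T1 score: D + G.
- Unadjusted change: D.
- T0-adjusted (ANCOVA): D + G − rG = D + (1 − r)G.

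If G = 0, all three estimate D without bias, but the cross-sectional test takes no account of chance imbalance at T0. If G ≠ 0, the cross-sectional test carries the whole gap.

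**Chance imbalance under random allocation.** The SD of the difference in T0 means is √(2/10) = 0.447. Then P(|difference| ≥ 0.5) = 2 × [1 − Φ(0.5/0.447)] = 0.264.

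**Residual variance, relative to a single score.** Change: 2(1 − r). T0-adjusted: 1 − r². Change is therefore noisier than the single score when r is below 0.5; the adjusted residual variance is always the smaller of the two.

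**Power when D = 1.0 and G = 0.** For the cross-sectional test the noncentrality is 1.0 × √(10/2) = 2.236 on 18 df, giving 0.562 at any r. The other columns are from simulation (400,000 runs per setting), which averages over chance T0 imbalance.

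| r | Cross-sectional | T0-adjusted | Unadjusted change |
|---|---|---|---|
| 0.3 | 56% | 58% | 43% |
| 0.5 | 56% | 66% | 56% |
| 0.7 | 56% | 82% | 78% |
| 0.8 | 56% | 93% | 92% |
| 0.9 | 56% | 99.6% | 99.7% |

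**False positives when D = 0 and G = 0.5.** For the cross-sectional test the noncentrality is 0.5 × √(10/2) = 1.118, giving 0.185.

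| r | Cross-sectional | T0-adjusted | Gap left in adjusted estimate, (1 − r) × 0.5 | Unadjusted change |
|---|---|---|---|---|
| 0.3 | 19% | 11% | 0.35 SD | 5% |
| 0.5 | 19% | 9% | 0.25 SD | 5% |
| 0.7 | 19% | 7% | 0.15 SD | 5% |
| 0.8 | 19% | 6% | 0.10 SD | 5% |
| 0.9 | 19% | 6% | 0.05 SD | 5% |

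With no T0 gap and equal change, all three tests hold 5%.

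**The case against.** **The comparison is ancillary.** This stands. Aims 1 and 2 each ask about one paradigm, Aim 3 asks about correlations, and no listed outcome is a contrast between paradigms. A reader might infer that the plan has no analysis of change. It has: the paired t-tests analyse T0 to T1 and T0 to T2 within groups. Only the difference in change between paradigms is missing.

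**Four groups are plainly meant.** This largely stands. A reader might take the label to mean that the primary test pools anodal and cathodal patients. The documents do not support that: they size 10 per experimental group, recruit separate sets of 10, and give each aim its own outcomes. The total of 20 AD and 20 bvFTD under Aim 3 is a head count, not an instruction to pool. The label needs clearer wording and no more.

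**Imaging is not left out.** This also stands. The paired tests speak of variables without excluding imaging, and Pearson correlations link clinical/cognitive change to imaging biomarkers. Only a between-paradigm imaging test is absent, and no aim calls for one.

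**The visit is unstated.** If the test were meant at T0, it would be a check of comparability and the false-positive figures would not apply. It would still say nothing about a difference in change.

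**The gain depends on r.** True. At r = 0.3 adjustment adds almost no power (58% against 56%), and the unadjusted change test does worse than the planned one (43%).

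**Conclusion.** The concern holds for the paradigm comparison. As written, it does not estimate whether change differs between stimulation and suppression, and this does not depend on r or the SD. If done after treatment, it passes any T0 difference straight into the result.

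The size of the loss rests on assumed values. For r from 0.5 to 0.9, T0 adjustment raises power for a 1.0 SD difference from 56% to between 66% and 99.6%; at r = 0.3 the gain is negligible. The false-positive rate of about 19% requires a true T0 gap of 0.5 SD, which the documents neither state nor rule out.

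This is a worthwhile improvement to a secondary comparison that the plan itself introduces. It is not a fault in the primary within-group tests, and the group label is a wording matter. Nor does the repair settle efficacy: with no sham or untreated patient group, and controls assessed at baseline only, a difference between paradigms would not show that tDCS caused either group's change.

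**What to change.** In the Statistical analysis section:

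1. Replace the cross-sectional paradigm test with: *Within AD and within bvFTD separately, change from T0 to T1 (and to T2) in clinical/cognitive scores will be compared between paradigms, adjusted for the T0 value (ANCOVA), with estimate and 95% CI.*
2. If allocation to paradigm is not random, also report the unadjusted difference in change, because the adjusted estimate keeps (1 − r) of a true T0 gap. State that the unadjusted test has less power than the planned one when r is below 0.5.
3. Do not treat a mixed-model visit-by-paradigm term as interchangeable with ANCOVA. With T0 means left free, it estimates the unadjusted contrast.
4. If imaging is added to this comparison, say which network's change is compared, since the paradigms target different networks within each diagnosis.
5. As a clarification only, have the paired-test sentence refer to each of the four diagnosis-by-paradigm groups (n=10).

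Cost: a few sentences and slightly more analysis work, with no new visits or data. ANCOVA adds the assumption of a common T0 slope in the two paradigms, besides normal residuals.

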#### **Clinical assessment**

Each patient will undergo a clinical and neuropsychological evaluation to assess symptoms and cognition at baseline (before tDCS session, T0) and follow-up (after the tDCS sessions, T1; and 6 months after tDCS treatment, T2). Patients will also undergo biological samples collection (CSF at T0, blood samples at T0, T1, T2) to assess the effect of tDCS on inflammatory measures (optional sub-study).

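### The only paradigm 1 versus 2 comparison names no follow-up visit and makes no use of T0, although the clinical outcomes are changes from T0

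*Combined protocol and SAP*

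**What the plan says.** The Statistical analysis section (B.e) gives the paradigm comparison one half-sentence: "Two-sample t-tests will be used for cross-sectional comparisons of clinical/cognitive scores between paradigm 1 and 2". The second half of that sentence applies the same test to "measures between the experimental groups and controls at baseline". No T1 or T2 is attached to the paradigm comparison, and no change score or covariate is mentioned. No other section plans a comparison of the two paradigms.

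The outcomes are defined differently. Under Aim 1, Outcome measures, the primary parameter is "change in scores at T1 compared with T0 for clinical and behavioural scores in AD and bvFTD patients". The secondary parameters include the T1 change in cognition and "change in scores at T2 compared with T0 for clinical, behavioural, and cognitive performance in AD and bvFTD patients". For Aim 2, "PRIMARY and SECONDARY efficacy parameters will be the same as in AIM1".

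T0 is available for everyone. The Aim 1 Clinical assessment section states "Each patient will undergo a clinical and neuropsychological evaluation to assess symptoms and cognition at baseline (before tDCS session, T0) and follow-up", and Aim 2 repeats the T0, T1 and T2 schedule. On how the second set of patients arises, Aim 2 says only "Ten mild AD and 10 mild bvFTD patients will be recruited and assessed following the procedures and inclusion/exclusion criteria described in AIM1". The supplied text states no method of allocating patients to a paradigm.

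Change from T0 is tested only within groups, by paired t-tests.

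**The concern.** A cross-sectional test at follow-up compares where the two groups end up, not how far they moved. Any T0 difference between the paradigms therefore enters the estimate. A stable difference carries over in full. A chance difference carries over multiplied by r, the correlation of T0 with the follow-up score.

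This matters because it is the only analysis that sets one treated group against another over the same period. The healthy controls are assessed at baseline only, and the paired tests have no comparator. A reader who wants to know whether stimulation or suppression did better has nothing else to use. Leaving the visit open also allows T1 or T2 to be chosen after the results are seen.

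**Working it through.** **The plan's own figure.** The plan gives n = 10 per experimental group and refers to earlier studies. It states no alpha, power, effect size or SD, so the figure cannot be reproduced. At an assumed two-sided 5% level and 80% power, 10 per arm corresponds to (1.960 + 0.842) × √(2/10) = 1.25 SD by the normal approximation, or 1.32 SD by the noncentral t.

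**Inputs.** From the documents: 10 patients per paradigm within each diagnosis, T0 measured in all. Assumed: two-sided 5% level, SD = 1 at both visits, approximate normality, r from 0.3 to 0.8, and illustrative T0 gaps of 0.25, 0.5 and 0.75 SD.

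**Standard errors of the paradigm difference.**
- Follow-up score only: √(2/10) = 0.447, 18 df.
- ANCOVA on T0: √[(2/10)(1 − r²)(17/16)], 17 df. The factor 17/16 is the cost of estimating the slope. At r = 0.5: √(0.2 × 0.75 × 1.0625) = 0.399.
- Change score: √[(2/10) × 2(1 − r)], 18 df. At r = 0.5: √(0.2 × 1) = 0.447.

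**Difference detectable with 80% power (SD units, noncentral t).**

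| r | Follow-up only | ANCOVA | Change score |
|---|---|---|---|
| 0.3 | 1.32 | 1.31 | 1.57 |
| 0.5 | 1.32 | 1.19 | 1.32 |
| 0.6 | 1.32 | 1.10 | 1.19 |
| 0.7 | 1.32 | 0.98 | 1.03 |
| 0.8 | 1.32 | 0.82 | 0.84 |

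ANCOVA breaks even with the plain t-test at r of about 0.26, and the change score at r = 0.5. At r = 0, ANCOVA needs 1.37 SD. With 8 per arm (an assumed loss; section B.f rates drop-out a medium risk but gives no rate), the figures are 1.51 SD for the t-test, 1.51 to 0.95 SD for ANCOVA and 1.78 to 0.95 SD for change scores.

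**Stable T0 gap, no treatment effect.** The part of the gap left in the estimate is all of it (follow-up only), 1 − r of it (ANCOVA) and none (change score). For a 0.5 SD gap the t-test has noncentrality 0.5/0.447 = 1.118 on 18 df and rejects 18.5% of the time. The ANCOVA and change-score rates below come from simulation with 100,000 trials per cell.

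| Gap (SD) | Follow-up only | ANCOVA, r = 0.3 | ANCOVA, r = 0.8 | Change score |
|---|---|---|---|---|
| 0.25 | 8.3% | 6.6% | 5.4% | 5% |
| 0.5 | 18.5% | 11.5% | 6.2% | 5% |
| 0.75 | 35.5% | 18.6% | 7.6% | 5% |

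**Chance T0 gap, no systematic difference.** The probability of a gap larger than g is 2[1 − Φ(g/0.447)], which is 0.58, 0.26 and 0.09 for g = 0.25, 0.5 and 0.75 SD. Given an observed gap of 0.5 SD, the expected error is r × 0.5 = 0.15 to 0.40 SD for the t-test, 0 for ANCOVA, and −(1 − r) × 0.5 = −0.35 to −0.10 SD for the change score. Averaged over chance gaps, all three methods reject 5%.

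**Skewed scores.** With rounded log-normal scores (log-SD 0.8, assumed) and no gap, all three reject about 4%, so none is inflated.

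**The case against.** - **Not a stated aim.** No aim or outcome is a difference between paradigms. Each aim asks whether one paradigm improves patients, and the paired tests answer that in the outcome's own terms. This stands: the comparison is ancillary, in a pilot.
- **Ambiguous sentence.** If 'at baseline' governs the whole sentence, the test is a T0 comparability check, for which a two-sample t-test is suitable. That reading is possible but less natural, because the phrase closes the separate clause on controls. Under it the plan contains no post-treatment paradigm comparison at all, so the section still needs clarifying.
- **The stable gap is hypothetical.** Eligibility is shared, and the milestones have a first patient finishing sessions under each paradigm in Month 1, which argues against successive cohorts. With chance gaps only, the planned test keeps its 5% level. This stands in part: a systematic gap is not shown, but without a stated allocation method it cannot be ruled out. The loss of precision when r exceeds about 0.26 does not depend on it.
- **ANCOVA is not always best.** It overtakes the plain t-test only above that r. Change scores edge ahead of it above about r = 0.87 with 10 per arm. That is correct, but at r = 0.9 the detectable differences are 0.597 and 0.593 SD, a gap of no practical weight.
- **Many models.** The Clinical assessment section in B.e lists about 17 measures. Two visits and two diagnoses make 17 × 2 × 2 = 68 models, plus as many change-score estimates. This is a fair reason to label the results exploratory. Most of these models replace t-tests that the current wording already implies.

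**Conclusion.** The concern holds. The sole between-paradigm analysis leaves its visit unspecified, does not use the T0 value already collected, and does not correspond to outcomes defined as change. It should be corrected, but it does not threaten the primary paired analyses.

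The gain in precision from using T0 depends on r: negligible at 0.3, and at 0.8 a fall in the detectable difference from 1.32 to 0.82 SD. The protection against a systematic T0 gap is real but partial with ANCOVA and complete with change scores. Both statements rest on the assumed error rate, equal SDs and range of r; none of these is in the documents. At 10 per arm the detectable difference exceeds 0.8 SD for every method at every tabulated r, so the comparison remains exploratory after correction.

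**What to change.** Replace the first half of the sentence in the Statistical analysis section with wording such as:

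> Within each diagnosis, paradigms 1 and 2 are compared at T1 (and, secondarily, at T2) by ANCOVA with the T0 value of the same measure as covariate, and the adjusted difference is reported with its 95% confidence interval. The difference in change from T0 is reported as a sensitivity analysis. T0 means and SDs are shown by paradigm. These comparisons are exploratory.

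Keep the two-sample t-tests for the baseline comparison with controls. If the team meant a baseline check only, it should say so and state whether it wants a post-treatment comparison as well.

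ANCOVA comes first because it is unbiased under a chance gap and more precise than change scores over the tabulated range. Change scores belong beside it because they fully remove a stable gap. If the two disagree, a systematic T0 gap is a likely explanation and should be discussed. Neither replaces a stated allocation method.

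Extending the model to rs-fMRI and ASL is optional and would add about 2 networks × 2 modalities × 2 visits × 2 diagnoses = 16 tests.

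Cost: two or three sentences, one degree of freedom per model, one extra estimate per comparison, and a small loss of precision if r is below about 0.25. No new data, visits or patients are needed.

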### **A. Background and State of Art**

Resting-state fMRI studies have shown that Alzheimer's disease (AD) is associated with the progressive degeneration of the default mode network (DMN), and behavioural frontotemporal dementia (bvFTD) with salience network (SN) degeneration (Pievani et al, 2011a). These 2 diseases also feature anti-correlated patterns (DMN connectivity is reduced and SN is hyper-activated in AD, while the opposite is seen in bvFTD; Zhou et al, 2010). Although DMN and SN disruption offer an attractive target for AD and bvFTD treatment, no study has investigated the efficacy of recalibrating these networks. Repetitive transcranial direct current stimulation (tDCS) and transcranial magnetic stimulation are non-invasive techniques capable to restore brain function through direct stimulation of disrupted networks or indirect suppression of hyper-activated networks (Cotelli et al, 2011; Naeser et al, 2005). In this pilot project we will test the efficacy of DMN and SN recalibration in AD and bvFTD through tDCS.

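### Baseline patient-control comparisons use unadjusted t-tests against controls comparable on age only, so any systematic sex, education or residual age difference would be read as, or would hide, a disease difference

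*Combined protocol and SAP*

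**What the plan says.** The Control group section states that "a group of 20 cognitively healthy controls of comparable age will be recruited", and gives their purpose: "For baseline comparison of clinical, cognitive, and imaging variables". It sets no criterion for sex or education, no age tolerance, and does not say whether age should be comparable to the AD patients, the bvFTD patients or both.

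The Statistical analysis section names two-sample t-tests for two jobs. One compares the paradigms among patients: "Two-sample t-tests will be used for cross-sectional comparisons of clinical/cognitive scores between paradigm 1 and 2". The other, at issue here, assesses "differences in clinical, cognitive, and neuroimaging measures between the experimental groups and controls at baseline". No covariate or regression model appears there.

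The Clinical assessment text under section e reads "The neuropsychological assessment will include the MMSE and specific tests for each cognitive domain", without mention of demographically corrected scoring. MRI analyses refers its connectivity procedure to a cited paper and states no covariates. Sex and education are not mentioned anywhere in the document.

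**The concern.** Controls are recruited separately from patients, so nothing in the design makes the expected demographic difference zero. Age comparability is the only safeguard, and it is loosely specified. If AD and bvFTD patients differ in age, one group of 20 cannot be closely comparable to both.

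A raw difference in means then estimates disease plus demographics. The demographic part can push a null measure towards significance or cancel part of a true difference. Modest contrasts, such as network connectivity, perfusion or some domain tests, are the most exposed. Section A describes the expected pattern as "DMN connectivity is reduced and SN is hyper-activated in AD, while the opposite is seen in bvFTD", and the imaging contrast with controls is where a reader would look for that pattern in these patients. What is at stake is the interpretation of a descriptive baseline comparison, not the treatment results.

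**Working it through.** **Inputs from the plan.** Controls: 20, one group. Patients: Aim 3 says "The subjects included in this analysis will be those recruited for AIM1 and AIM2 (20 AD and 20 bvFTD", so each diagnosis has 20. The test is an unadjusted two-sample t-test.

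**Assumed, because the plan gives no figure.** Two-sided alpha 5%; an age offset of 3 to 4 years at 0.03 to 0.05 SD of outcome per year; an education gap of 3 years at 0.10 to 0.15 SD per year.

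**The plan's own figure.** Ten per experimental group is justified by earlier studies, with no effect size, SD, alpha or power, so it cannot be reproduced. This point does not dispute it.

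**Step 1: bias = gap × slope.**
- Age: 3 × 0.03 = 0.09 SD to 4 × 0.05 = 0.20 SD.
- Education: 3 × 0.10 = 0.30 SD to 3 × 0.15 = 0.45 SD.

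**Step 2: rejection rate with no true disease difference, 20 versus 20.** SE = sqrt(1/20 + 1/20) = 0.316 SD. The rate comes from the noncentral t with 38 df and noncentrality bias/0.316.

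| Bias (SD) | Noncentrality | Rejection rate |
|---|---|---|
| 0 | 0 | 5.0% |
| 0.10 | 0.32 | 6.1% |
| 0.20 | 0.63 | 9.5% |
| 0.30 | 0.95 | 15.2% |
| 0.45 | 1.42 | 28.4% |

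**Step 3: masking.** At 20 versus 20, a true difference of 0.91 SD has 80% power. An opposing age bias of 0.10 to 0.20 SD leaves 0.81 to 0.71 SD, with power of 70% to 59%. An opposing bias of 0.30 to 0.45 SD leaves 0.61 to 0.46 SD, with power of 47% to 29%.

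**Step 4: does adjustment repair it?** A simulation with 20,000 replicates per setting and no disease effect shifted a covariate by s SD between groups, with correlation r to the outcome (expected bias r × s). Results at 20 versus 20:

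| s | r | Unadjusted error | Adjusted error |
|---|---|---|---|
| 0 | 0.3 | 4.8% | 4.7% |
| 0.5 | 0.3 | 7.5% | 5.1% |
| 0.5 | 0.5 | 12.0% | 5.2% |
| 1.0 | 0.3 | 15.4% | 4.9% |
| 1.0 | 0.5 | 33.6% | 4.9% |

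The adjusted bias was close to zero throughout. With no systematic shift the plain t-test is valid, so the problem is conditional on one.

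**Step 5: precision.** With balanced covariates, adjustment multiplies the SE by sqrt(1 − R²): 0.95 at R² = 10% and 0.84 at R² = 30%. With a covariate shift of 0.75 SD, the group SE is also inflated by sqrt(1 + 0.25 × 0.75²) = 1.07. The net change is 1.07 × 0.95 = 1.01 (about 1% worse) to 1.07 × 0.84 = 0.89 (about 11% better). The full precision gain and the bias problem therefore do not occur together.

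**The case against.** The best case for leaving the plan alone is that this is a descriptive contrast in a pilot. It appears in none of the outcome lists under Aims 1 to 3, all of which are changes from T0 within patients. That stands, and it limits the point.

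Four stronger readings are tempting, and the documents do not support them.

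- **The comparison validates the stimulation targets.** A reader might infer this from section A. No section gives it that role: the rationale is drawn from earlier literature, paradigms are assigned by diagnosis, and the timeline starts tDCS in month 1, so the comparison gates nothing.
- **False-positive rates reach 15 to 28%.** These come from the assumed education gap. Education bears mainly on clinical and cognitive scores and is not among the covariates proposed for imaging. For the core clinical and cognitive measures, such as CDR and MMSE, diagnosed dementia is set against cognitively healthy controls, so the null is false by selection. The bias there mainly changes the size of an expected difference.
- **Each test is 10 versus 20, and pooling buys precision.** The sample-size sentence does read "Sample size for this pilot study (n=10 subjects for each experimental group) has been determined on the basis of previous tDCS". But the t-test sentence compares the two paradigms within the experimental groups, so the term there must cover both paradigms, and Aim 3 counts 20 per diagnosis. The usage is ambiguous, so no gain (SE 0.387 to 0.316 SD) can be claimed.
- **Bias is certain.** It needs a systematic imbalance, and the plan contains no data on sex, education or the age difference between AD and bvFTD patients.

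Covariates inside the cited imaging procedures cannot be excluded either, but the plan does not state them. None of this gives a reason to prefer the unadjusted test when controls are not randomised.

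**Conclusion.** The concern holds in a limited, conditional form. The planned test makes no allowance for demographics, and age is the only comparability criterion, applied to one control group for two diseases. Any systematic difference in sex, education or residual age that relates to a measure would be counted as, or would mask, a disease difference.

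For an assumed age bias of 0.1 to 0.2 SD, the nominal 5% error becomes about 6 to 9.5% at 20 versus 20. For cognitive scores, the assumed 0.30 to 0.45 SD education bias is chiefly an error in the reported magnitude. No specific bias was derived for sex. All gaps and slopes are assumptions. Large differences, such as MMSE, are unlikely to change direction; modest imaging and domain-test differences are the ones at risk. Primary and secondary outcomes, including the imaging changes in Aim 3, do not use controls and are unaffected. The change is worth making because it is cheap and the named test is the weaker choice, not because the trial's efficacy conclusions depend on it.

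**What to change.** In the Statistical analysis section, replace the patient-control t-tests with one linear model per measure:

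- **Group factor:** AD, bvFTD and control. State explicitly that the two paradigm groups within a diagnosis are pooled at T0, since the term for experimental groups is used in two senses.
- **Covariates:** age and sex for imaging measures; age, sex and, if recorded at T0, education for clinical and cognitive scores.
- **Reporting:** adjusted AD-control and bvFTD-control differences with 95% CIs, alongside a table of demographics by group.

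The cost is wording plus 2 to 3 degrees of freedom out of 60 − 3 = 57. Education may need to be added to the T0 record, as the plan does not say that it is collected. The sample size does not change. Any precision gain is small and may vanish if covariates are imbalanced, so the benefit to claim is removal of bias.
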